### 10.8.1 Key Secondary Endpoint

#### 10.8.1.1 *Change from baseline in AISRS at Week 2*

The change from baseline (see Section 8.1.2) to Week 2 in AISRS Score will be analyzed using the same estimand and imputation process as the primary endpoint. The linear mixed effects model analysis of covariance (ANCOVA) with the change from baseline in the AISRS score at Week 2 following randomization as dependent variable, and treatment group, baseline score of AISRS, sex and age as fixed effects will be used in current analysis. The outcome will be considered confirmatory, if in agreement with the primary endpoint outcome and provided that the null hypothesis is rejected for the primary outcome. This gatekeeping function of the primary outcome allows to avoid any adjustment for multiplicity of testing.

### 10.8.2 Other Secondary Endpoints

#### 10.8.2.1 *Change in CGI-S from baseline to Week 2 and Week 6*

The change from baseline (see Section 11.2) to Week 2 and Week 6 will be summarized descriptively.

The proportion of subjects having improved or having worsened/being stable will be calculated at each post-baseline assessment by treatment group. The proportion difference and the relative risk (LSD over placebo) with 2-sided 95% CIs will be displayed. The proportion of subjects in each category will be calculated at each post-baseline assessment based on the number of subjects with non-missing CGI-S score.

A listing of CGI-S values over time will be provided for the FAS population.

#### 10.8.2.2 *Change from baseline in ASRS and CAARS-L-SR to Week 2, 4 and 6*

The change in ASRS and CAARS-L-SR from baseline (see Section 11.2) to Week 2, 4 and 6 will be analyzed descriptively as indicated in section 8.9.1**Error! Reference source not found.** (in addition, the 95% confidence interval for the mean and median will be reported).

Separate listings of ASRS and CAARS-L-SR values overtime will be provided for the FAS.

## 10.9 PHARMACOKINETICS

The analyses of pharmacokinetic (PK) endpoints will be performed on the PKS (see definition in Section **Error! Reference source not found.**) population. The actual sampling time will be used for PK parameter calculation and graphical presentation of individual data.

### 10.9.1 Pharmacokinetic Parameters

The following PK parameters will be determined by non-compartmental analysis using individual concentration-time profiles:

**Table 7. Plasma Pharmacokinetic Parameters**

Parameter, Units	Definition	Method of Determination
------------------	------------	-------------------------

$C_{\max}$ , (ng/ml)	Maximum observed drug concentration	Observed value
$t_{\max}$ , (h)	Time to reach $C_{\max}$	Actual elapsed time for observed $C_{\max}$ in each period
$AUC_{0-t}$ , (ng·hr/ml)	Area under the concentration-time curve from time zero to the measurable concentration time $t$	$AUC_{0-t}$ will be calculated using the linear-up log-down trapezoidal interpolation method
$AUC_{0-\infty}$ ,	Area under the concentration-time curve from time zero to infinity (extrapolated)	$AUC_{0-\infty}$ (extrapolation of the $AUC_{0-t}$ ) will be calculated as $AUC_{0-t} + \frac{C_t}{\lambda_t}$ , where $C_t$ is the last observed measurable concentration.
$AUC_{0-0.5h}$	Area under the drug concentration-time curve from time zero to time 0.5h	Calculated using linear-up log-down trapezoidal summation from time zero to 0.5 hour post MM-120 administration
$AUC_{0-1h}$	Area under the drug concentration-time curve from time zero to time 1h	Calculated using linear-up log-down trapezoidal summation from time zero to 1 hour post MM-120 administration
$AUC_{0-2h}$	Area under the drug concentration-time curve from time zero to time 3h	Calculated using linear-up log-down trapezoidal summation from time zero to 2 hours post MM-120 administration
$AUC_{0-3h}$	Area under the drug concentration-time curve from time zero to time 3h	Calculated using linear-up log-down trapezoidal summation from time zero to 3 hours post MM-120 administration
$AUC_{0-4h}$	Area under the drug concentration-time curve from time zero to time 4h	Calculated using linear-up log-down trapezoidal summation from time zero to 4 hours post MM-120 administration
$AUC_{0-6h}$	Area under the drug concentration-time curve from time zero to time 1h	Calculated using linear-up log-down trapezoidal summation from time zero to 6 hours post MM-120 administration
$t_{1/2}$ , (hr)	Terminal elimination half-life	$\ln(2)/\lambda_z$ , where $\lambda_z$ is the first-order rate constant of drug associated with the terminal portion of the curve, see definition below.
$\lambda_z$	The observed elimination rate constant	Estimated by linear regression through at least three data points (not including $t_{\max}$ ) in the terminal phase of the log concentration-time profile; see additional criteria below.

#### **10.9.1.1 Additional criteria for the observed elimination rate constant ( $\lambda_z$ ) determination.**

This parameter will be the negative of the estimated slope of the linear regression of the ln-transformed concentration versus time profile in the terminal elimination phase (log-linear regression after semilogarithmic transformation of the data using at least the last 3 data points of the terminal linear phase of the concentration-time curve.). Best fit method will be used to calculate the  $\lambda_z$  from at least 3 concentration data points including only data points after  $C_{max}$  ( $t_{max}$ ). Rsq adjusted, the goodness of fit statistic for the terminal elimination phase, adjusted for the number of points used in the estimation of  $\lambda_z$  must be  $\geq 0.8$ . If the  $\lambda_z$  cannot be measured (e.g.: fewer than 3 non-zero concentrations in the terminal elimination phase or Rsq adjusted  $< 0.8$ ), the PK parameters derived from  $\lambda_z$  will not be reported for that individual PK profile ( $AUC_{0-inf}$ , and  $t_{1/2}$ ). The timepoint where ln-linear  $\lambda_z$  calculation begins ( $\lambda_z$  Lower) and the actual sampling time of the last measurable concentration used to estimate the  $\lambda_z$  ( $\lambda_z$  Upper), as well as the Rsq adjusted for the ln-linear regression for the calculation of the elimination rate constant will be reported.

#### **10.9.2 Handling of Below Lower Limit of Quantification (BLOQ) values**

Concentration BLOQ will be imputed by 0 for the calculation of descriptive statistics, PK analyses and graphical presentation except for the geometric mean and the geometric CV, where it will be imputed as Lower Limit of Quantification (LLOQ)/2.

If the concentrations before the first quantifiable concentration time point is BLOQ, the concentration will be set to 0.

If the concentrations after the last quantifiable concentration time point is BLOQ, the concentration will be set to missing.

If there are embedded BLOQ values between quantifiable concentrations, these BLOQ values will be set to missing.

If there is a quantifiable concentration after 2 consecutive BLOQ values at the end of the profile, this quantifiable concentration and any further quantifiable concentration will be set to missing.

Handling of other potential anomalies in the serum PK profiles will be discussed with the sponsor before PK parameter derivation.

#### **10.9.3 Summary Statistics**

Summary statistics include n, arithmetic mean, standard deviation (SD), geometric mean, coefficient of variation (CV), median, minimum and maximum. The CV will be expressed as a percentage and calculated as follows:

$$CV \text{ of the arithmetic mean (\%)}: \frac{SD}{mean} \times 100$$

$$CV \text{ of the geometric mean (\%)}: \sqrt{\exp(\text{variance for log transformed data}) - 1} \times 100$$

A table with summaries on PKS at “Week 1 D1” (first drug administration visit) will be presented with the following information:

- MM-120 plasma concentrations;

A table with summaries on PKS and in accordans with the definitions in Table 7 will be presented with the following information:

- Terminal elimination half-life  $t_{1/2}$ (hours)
- $C_{max}$ ;
- $t_{max}$ ;

- AUC;

Individual plots of MM-120 concentrations over actual sample time with all subjects on the same plot and separately per each subject's PK profile will be generated using linear and semi-logarithmic scales (i.e. log y-axis) on PKS and sampling time (pre- and post-dose).

Listings of individual MM-120 plasma concentrations and all parameters defined in Table 7 will be produced on PKS.

## 10.10 PHARMACODYNAMICS

Pharmacodynamic analysis (unless explicitly specified) will be performed on FAS population, in each treatment group.

Pharmacodynamic descriptive statistics will include: n, mean, standard deviation, Q1 (25th percentile), Q3 (75th percentile), minimum, maximum, and 95% Confidence Interval for the mean and for the median.

### 10.10.15 Dimensions of Altered States of Consciousness scale (5D-ASC).

5D-ASC will be assessed at Week 1 Day 1 and Week 6, 6 hours after dosing (see Section 2.1.2). The scale consists of 94 items (questions) and is scored on a 0-100 mm VAS extrapolated to 100% scale for quantitative evaluation. Each item of the scale corresponds to one of the 5 dimensions defined below. The descriptive statistics, as defined above, will be shown for 5 5D-ASC dimensions:

- 1) Oceanic boundlessness – summation of questions 1, 3, 9, 12, 16, 18, 26, 34, 35, 36, 40, 41, 42, 45, 50, 52, 57, 62, 63, 69, 71, 73, 81, 86, 87, 91, and 94. Maximum value = 2700.
- 2) Anxious ego dissolution – summation of questions 6, 8, 21, 27, 32, 38, 43, 44, 46, 47, 53, 56, 60, 64, 67, 78, 79, 80, 85, 88, and 89. Maximum value = 2100.
- 3) Visionary destructuralization – summation of questions 7, 14, 20, 22, 23, 28, 31, 33, 39, 54, 58, 70, 72, 75, 77, 82, 83, and 90. Maximum value = 1800.
- 4) Auditory alterations – summation of questions 4, 5, 11, 13, 19, 25, 30, 48, 49, 55, 65, 66, 74, 76, 92 and 93. Maximum value = 1600.
- 5) Vigilance reduction – summation of questions 2, 10, 15, 17, 24, 29, 37, 51, 59, 61, 68, and 84. Maximum value = 1200.

The 5D-ASC Total Score will be calculated as the sum of all the questions. The maximum value for the Total Score is 9400.

Additionally, the number (%) of completers and non-completers of the questionnaire will be evaluated by the answer 'Yes|No' to the question 'Was the 5D-ASC questionnaire completed by the subject?' respectively and will be presented in the summary table. The data are collected in the '5D-ASC' CRF section.

A spider-plot will be produced for graphical representation of 5 5D-ASC dimensions described above. The mean of the scores in 5 dimensions defined above standardized to 0-100 scale (eg, 'Vigilance reduction' mean/1200\*100) will be displayed on the spider plot.

A listing of the 5D-ASC subscales and Total Score will be provided.

### 10.10.2 Mystical Experience Questionnaire (MEQ), drug effect Visual Analog Scale (VAS).

Mystical Experience Questionnaire (MEQ) will be assessed at Week 1 Day 1 and Week 6, 6 hours after dosing (see Section 1.2.2). The descriptive statistics, as defined above, will be shown for 4 MEQ scores and Total score (expressed on 100% scale):

- 1) Transcendence;
- 2) Positive mood;
- 3) Ineffability;
- 4) Mystical;
- 5) Total score.

Additionally, the number (%) of completers and non-completers of the questionarie will will be evaluated by the answer 'Yes|No' to the question 'Was the MEQ 30 questionnaire completed by the subject?' respectively and will be presented in the summary table. The data are collected in the 'MEQ-30' CRF section.

Box plot showing the distribution of MEQ scores in each treatment group will be produced.

Visual Analog Scale (VAS) will be assessed at Baseline, at 0, 0.5, 1, 2, 3, 4 and 6 hours after dosing (see Section 2.1.2). The following 9 items will be used in VAS (0-100 mm) assessment of the score:

- 1) Any drug effect;
- 2) Good drug effect;
- 3) Bad drug effect;
- 4) Drug liking;
- 5) Fear;
- 6) Nausea;
- 7) Alteration of vision;
- 8) Alteration of sense of time;
- 9) The boundaries between myself and my surroundings seem to blur.

The descriptive statistics of scores (extrapolated to 100% scale) will be presented for each time point of assessment in each treatment group and overall.

Additionally, the number (%) of completers and non-completers of the questionarie will will be evaluated by the answer 'Yes|No' to the question 'Was the VAS questionnaire completed by the subject?' respectively and will be presented in the summary table. The data are collected in the 'VAS' CRF section.

## **10.11 EXPLORATORY ENDPOINTS**

Sleep quality/duration data are collected in the "Sleep Quality" CRF section and will be analyzed on FAS as continuous and categorical variable by treatment and visit as described in Section 8.10.

## **10.12 SAFETY ENDPOINTS**

The AEs (adverse events) will be tabulated according to their System Organ Class (SOC) and Preferred Term (PT), in accordance with the Medical Dictionary for Regulatory Activities (MedDRA) coding.

### **10.12.1 Adverse events**

Adverse events (AEs) will be summarized for treatment emergent adverse events (TEAEs). TEAEs are defined as AEs that occur on or after the day of the first dose. MedDRA terminology will be used to classify all AEs with respect to system organ class (SOC) and preferred term (PT).

A summary of subjects with TEAEs will be presented for each treatment group. The summary will include counts and percentages for subjects who experience at least one AE, overall and by SOC and PT. This will be repeated for severe TEAEs, related TEAEs and serious TEAEs. Severity will be captured as Grade 1 through Grade 5 with Grades 3-5 categorized as severe. Related will be captured

as: none, unlikely, possibly or probably, with related = possibly or probably. Serious will be captured with the standard serious adverse event (SAE) criteria.

The summary tables will be presented in descending order according to the incidence in the 'All' group (e.g., SOC and PT within each SOC with the highest number of occurrences will appear first). Equal frequency of different SOC/PTs will be sorted in alphabetical order of the SOC/PT.

Subjects who report the same PT on multiple occasions will be counted once for the preferred term under the highest severity when summarizing by severity, under the closest relationship to the drug when summarizing by relationship, under most serious when summarizing by seriousness.

Separate summary tables by SOC and PT will be provided for: TR-TEAEs, SAEs, and AEs leading to premature treatment discontinuation.

Individual subject listings will be provided on SAF.

#### **10.12.1.1 Subgroup analysis**

TEAEs, SAEs, AEs related to the study drug and AEs leading to premature treatment discontinuation will be tabulated on SAF by preferred term (PT) by treatment phase as follows:

- **Days of dosing:** all AEs occurred on same date/visit of treatment but only during or after administration of study drug (with time on or after treatment administration). Week 1 D1 (Dose 1), Week 1 D5 (Dose 2), Week 2 D8 (Dose 3), Week 2 D12 (Dose 4), Week 3 D15 (Dose 5), Week 3 D19 (Dose 6), Week 4 D22 (Dose 7), Week 4 D26 (Dose 8), Week 5 D29 (Dose 9), Week 5 D33 (Dose 10), Week 6 D36 (Dose 11), Week 6 D40 (Last dose 12);

This information will be pooled in summary table, i.e. all AEs occurred on/after all doses: first, second etc. until last dose; as well as will be summarized separately, i.e. AEs occurred on/after each dose: on/after first dose, on/after second dose etc. and until on/after last dose.

- **Non-dosing days:** (a) all AEs with the date different from treatment administration date/visit defined above and until Week 10 Follow-up visit. (b) all AEs which occurred prior to study drug administration (with time before administered dose) on dosing days.

This information will be pooled in summary table, i.e. all AEs occurred between doses: first and second, second and third etc. until Week 10 Follow-up visit (EOS) or until Early Termination (ET) whatever comes earlier, as well as will be summarized separately, i.e. split by periods between doses: Dose 1 - Dose 2, Dose 2 - Dose 3, Dose 3 - Dose 4, Dose 4 - Dose 5, Dose 5 - Dose 6, Dose 6 - Dose 7, Dose 7 - Dose 8, Dose 8 - Dose 9, Dose 9 - Dose 10, Dose 10 - Dose 11, Dose 11 - Dose 12, Dose 12 | last administered Dose - EOS | ET.

In case of missing dates, the rules defined in Section 11.3.3 will be applied. In case of missing time of the AE or the treatment administration on the same day, the AE will be considered as occurred after the treatment administration, meaning will be summarized in 'Days of dosing' category.

Frequency statistics will be presented by treatment group. The summary tables will be presented in descending order according to their incidence in the active treatment group of 'Days of dosing' treatment phase (e.g., individual preferred term with the highest number of occurrences appear first) sorting ties alphabetically.

#### **10.12.2 Vital signs**

Vital signs (defined in section 8.11.4), including changes from baseline (defined in section 11.1.1), will be listed and summarized on the SAF for each parameter separately, using descriptive statistics

for continuous data. In the evaluation of the absolute changes from baseline, only subjects with both the baseline and specific time point assessment will be included.

### **10.12.3 Resting 12-lead ECG**

12-lead ECG parameters (defined in section 8.11.5) will be separately listed and summarized on SAF, using descriptive statistics for continuous data, absolute values and corresponding change from baseline at each time point.

Treatment emergent ECG abnormalities (see definition in Section 8.11.5) will be summarized.

### **10.12.4 Laboratory**

Clinical laboratory data, abnormalities (defined in section 8.11.3) will be summarized on SAF.

The percentage of subjects with values beyond clinically important limits will be summarized by frequency tables and shift tables (Normal, Abnormal not clinically significant, Abnormal clinically significant), as well as the abnormalities in general. Data will be also summarized for the absolute value and corresponding change from baseline at each scheduled assessment, using respective SI units.

Individual listings will be produced for all parameters reporting flags of abnormal or out-of-range values.

Listings of pregnancy test results will be presented.

### **10.12.5 Physical examination**

All physical examination data will be listed on SAF by visits (Baseline, Week 6 and Week 10), with associated general assessment. If an abnormality is found, further details describing the signs and symptoms related to the abnormality will be specified.

### **10.12.6 Columbia-Suicide Severity Rating Scale**

Columbia-Suicide Severity Rating Scale will be listed at Baseline, Week 2 D8, Week 2 D12, Week 3 D15, Week 3 D19, Week 4 D22, Week 4 D26, Week 5 D29, Week 5 D33, Week 6 D36, Week 6 D40, Week 10 Follow-up/Final visit for withdrawals on SAF.

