7.2.3. Columbia-Suicide Severity Rating Scale

The Columbia-Suicide Severity Rating Scale (C-SSRS) is a validated outcome assessment that assesses a subject's suicidal ideation or behavior over a specified time interval (Posner et al., 2011). Suicidal ideation is assessed on a scale from 1 (wish to be dead) to 5 (active suicidal ideation with specific plan and intent). Suicidal behavior is assessed based on responses to individual prompts about prior suicidal actions. The C-SSRS will be assessed at all study visits.

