13.6.7.2 Other safety parameters

Safety outcomes, including vital signs, laboratory parameters' values, ECG parameters and abnormalities, will be reported by treatment arm. All safety data (scheduled and unscheduled) will be presented in the data listings. Continuous variables will be summarized using descriptive statistics (n, mean, SD, minimum, median, and maximum) by treatment/dose group at relevant timepoints. Categorical variables will be summarized in frequency tables (frequency and proportion) by treatment/dose group at relevant timepoints. Graphical presentations will be used as appropriate.

Where applicable, data will be summarized for the absolute value at each scheduled assessment and for the corresponding change from baseline. For clinical laboratory tests, listings of values for each subject will be presented with abnormal or out-of-range values flagged. The percentage of subjects with values beyond clinically important limits will be summarized by frequency tables and shift tables.

Treatment emergent ECG abnormalities will be summarized similarly to AEs.

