## 8.11 SAFETY ENDPOINTS

The evaluation of safety of study drug will be done considering the following variables:

- Adverse events ('Adverse Event' CRF section);
- Safety laboratory evaluation and Urine pregnancy testing ('Blood sample' and [REDACTED] sections of the CRF);
- Vital signs, i.e. supine blood pressure, body temperature, heart rate, respiratory rate ('Vital signs' CRF section);
- 12-lead safety ECG ('12-Lead ECG' CRF section);
- Columbia-Suicide Severity Rating Scale (C-SSRS, 'C-SSRS SLV' CRF section).

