#### **8.11.7 Columbia-Suicide Severity Rating Scale**

Columbia-Suicide Severity Rating Scale is collected at Screening (C-SSRS SCN CRF page) at Baseline, Week 2 D8, Week 2 D12, Week 3 D15, Week 3 D19, Week 4 D22, Week 4 D26, Week 5 D29, Week 5 D33, Week 6 D36, Week 6 D40, Week 10 Follow-up/Final visit for withdrawals (C-SSRS-SLV CRF page).

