## 10 STATISTICAL ANALYSIS

### 10.1 GENERAL STATISTICAL METHODOLOGY

Unless otherwise specified:

- Parameters will be shown in tables and listings according to the CRF order;
- In summary tables, all subjects will be grouped by treatment group; the 'LSD' treatment group will be displayed in the first column and 'Placebo' in the second; a 'total' column (including the two treatment groups) may be added in some tables as specified in TLF layouts section;
- Continuous numerical variables will be summarized using the following descriptive statistics: n, mean, standard deviation (SD), median,  $Q_1$  (25th percentile),  $Q_3$  (75th percentile), minimum, and maximum;
- Categorical including ordinal variables will be summarized by frequency and incidence;
- All statistical tests (unless explicitly specified) will be carried out at a significant level ( $\alpha$  level) of 0.05, two-tailed 95% Confidence Interval (CI) will be reported.
- Listings include data from scheduled and unscheduled assessments;
- All listing will be ordered by Treatment, Subject ID, visit/date/time (where applicable).

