#### 12.8.4 Columbia-Suicide Severity Rating Scale

Output name	Display*	Title (Description)	Analysis set(s)**	Key deliverable	Mock layout	SAP section
LCSSRS	L	Subject listing of Columbia-Suicide Severity Rating Scale	SAF		Layout L28	10.12.6

\* S=Summary table, L= Listing, F=Figure, \*\* SCR=Screened set, FAS=Full Analysis set, SAF=Safety set, RAN=Randomized set, PPS=Per protocol set, PKS=Pharmacokinetic analysis set

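### The C-SSRS is a named safety endpoint with a listing as its only output, so no C-SSRS-based count by arm is planned, and three C-SSRS visit lists in the SAP omit Week 1 D5

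*SAP*

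**What the plan says.** Protocol 3.2.2 lists the C-SSRS among the safety endpoints. Protocol 7.2.3 states "The C-SSRS will be assessed at all study visits", and 6.2.4.2 requires the since-last-visit (SLV) version at each twice-weekly dosing visit. SAP 8.11 names the same endpoint: "Columbia-Suicide Severity Rating Scale (C-SSRS, 'C-SSRS SLV' CRF section".

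For analysis, SAP 10.12.6 begins "Columbia-Suicide Severity Rating Scale will be listed at Baseline, Week 2 D8" and goes on to Week 10. The output list in SAP 12.8.4 has one entry, "Subject listing of Columbia-Suicide Severity Rating Scale", of type L, on the safety set, with Layout L28.

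Two general rules bear on this. Protocol 13.6.7.2 says "Categorical variables will be summarized in frequency tables (frequency and proportion) by treatment/dose group at relevant timepoints". SAP 10.1 says "Categorical including ordinal variables will be summarized by frequency and incidence", but that section applies only where nothing else is specified. SAP 10.1 also says "Listings include data from scheduled and unscheduled assessments", and SAP 2.1.3 repeats that rule for subject listings.

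**The concern.** Protocol 7.2 places the main safety worry with this drug class on the psychological side, and 7.2.1 says that controlled studies of repeated low dosing give no evidence on psychological effects. Vital signs, ECG and laboratory data all have summary tables by arm (SAP 12.8.2, 12.8.3, 12.8.5). The suicidality scale has none.

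A reader could count cases from L28, which shows treatment. The rules for that count are not fixed in advance: which visits are used, whether the worst category is taken, and what pre-dose level it is compared with.

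The missing Week 1 D5 visit matters because the SLV form looks back to the previous visit. If that form is left out, the next listed form (Week 2 D8) looks back only to D5. The interval after the first dose would then appear on no listed form.

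**Working it through.** No power or alpha figure is involved. The check compares the passages and counts visits.

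**Outputs.** SAP 12.8.4 plans one listing and no table or figure. None of table layouts T1 to T30 is for the C-SSRS. The adverse event tables (SAP 10.12.1 and 12.8.1, Layouts T4 and T8) count by arm any ideation or behaviour recorded as an adverse event. Protocol 7.6.1 defines adverse events broadly enough to include a clinically significant change from baseline. Neither document makes a positive C-SSRS answer a trigger for an adverse event report, so these tables do not replace a count from the scale.

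**Visit lists that omit Week 1 D5.**
- SAP 8.11.7: "Columbia-Suicide Severity Rating Scale is collected at Screening (C-SSRS SCN CRF page) at Baseline, Week 2 D8, Week 2 D12", and onward to Week 10.
- SAP 10.12.6: the same run of visits without Screening.
- L28 programmer note (SAP 13.2.29): the same run as 10.12.6.

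After Screening, each names Baseline + 10 dosing visits (Week 2 D8 to Week 6 D40) + Week 10 = 12 visits.

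**Places that include Week 1 D5.**
- SAP Table 1 marks the SLV form under twice-weekly dosing.
- SAP 2.1.3 says the C-SSRS is evaluated at each twice-weekly visit.
- SAP Table 3, headed for vital signs and C-SSRS, has a Week 1 D5 row (days 2 to 6) and 13 visit rows in all.
- Protocol 6.2.4.2 requires the form at each dosing visit, and SAP 10.12.1.1 identifies Week 1 D5 as Dose 2.

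Difference: 13 − 12 = 1 visit, Week 1 D5.

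**Forms that could be left out of the listing**, assuming all 52 randomised subjects attend that visit:
- If the all-assessments rule in SAP 2.1.3 and 10.1 governs: 0.
- If the three visit lists govern: 1 × 52 = 52, or 26 per arm.
- If the CRF has no SLV page at that visit: there is no form to omit, but an assessment that the protocol requires was not captured.

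**Pre-dose comparator.** Exclusion criterion 6 defines excluded ideation as a score of 2 or greater, so a subject with score 1 can enter. Under the last-value baseline in SAP 11.1.1.8, the comparator would be the Day 1 pre-dose form, which looks back at most 3 + 1 = 4 days to the Baseline visit. The Baseline form looks back up to 4 weeks to Screening. Neither covers ideation reported at Screening itself. A subject scoring 1 at Screening, 0 on both pre-dose SLV forms and 1 after dosing would be classed as worse.

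**The case against.** The listing looks like a deliberate choice: the SAP version history records the C-SSRS analysis as an addition in version 2.0. Physical examination and pregnancy tests are also listing-only. The trial has 52 subjects, excludes anyone with a lifetime suicide attempt, and plans no inference on safety. L28 shows every ideation and behaviour item with the treatment, and positive answers can be filtered by program. Reading effort is therefore no measure of harm. This argument stands in part: if positive forms are few, the listing shows each case. The documents give no expected rate, however, and a pre-specified count, even a zero in each arm, is a clearer safety result.

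A reader might infer that the plan breaks a protocol commitment. The documents do not support that. Protocol 13.6.7.2 names vital signs, laboratory and ECG but not the C-SSRS, and the SAP 10.1 default gives way to the listing specified in 10.12.6.

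On Week 1 D5, three matching lists are compatible with a CRF that has no SLV page at that visit. The annotated CRF is not among the documents. Table 3 is shared with vital signs, so its D5 row does not by itself prove that a C-SSRS form exists. This stands as a reason to check the CRF first. It does not remove the conflict with SAP Table 1, SAP 2.1.3 and protocol 6.2.4.2.

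**Conclusion.** Both parts hold, as a minor safety-reporting point. The plan has 1 listing and 0 of 30 table layouts for the C-SSRS, so no C-SSRS-based count by arm is planned. It would be too strong to say that nothing counts suicidality by arm, because the adverse event tables do so for whatever is reported as an adverse event.

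The Week 1 D5 omission is a contradiction within the SAP and with the protocol. Its effect lies between 0 and 52 forms missing from the only C-SSRS output. The upper figure assumes that the CRF has the form, that all 52 subjects attend, and that the programmer follows the lists literally. A reader might infer that these data are lost, but the documents do not settle which rule governs, and the loss may be nil.

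**What to change.** 1. Check the annotated CRF, then add Week 1 D5 to SAP 8.11.7, SAP 10.12.6 and the L28 note so that they match Table 3. If the CRF has no form at that visit, report this as a departure from the protocol.
2. Add one descriptive table on the safety set by arm, with no test. Give n (%) of subjects with any post-dose suicidal ideation by worst category (1 to 5), and n (%) with any post-dose suicidal behaviour. Use all post-dose forms from Week 1 D5 to Week 10 or early termination.
3. A worsening row is optional. If it is added, compare with the worst pre-dose ideation across three sources: the recent-ideation period of the Screening form, the Baseline SLV form and the Day 1 pre-dose SLV form. State this as an exception to SAP 11.1.1.8. The documents do not describe the Screening form's recall periods, so the SAP should name the one used. Otherwise leave the row out.

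The cost is three corrected lists and one table from assessments the protocol already schedules. No new assessment is needed, and efficacy, alpha and power do not change.
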